Primary outcome	Variable	1. Carer wellbeing
	Measure (instrument, scale)	1. Carer self-reported wellbeing using the Warwick Edinburgh Mental Wellbeing Scale (Tennant et al., 2007) within an online survey
Secondary outcome(s)	Variables	2. Perceived peer support 3. Mental health of children in fostering and kinship households 4. Family relationships 5. Placement stability
	Measure(s) (instrument, scale)	2. Self-reported number of other local carers a foster carer or kinship carer reports they are able to contact for help if needed (0+) (self-reported perceived peer support) asked within an online survey 3a. Carer-reported child wellbeing using the Brief Assessment Checklist for Children and Adolescents (20 item) (Tarren-Sweeney, 2013) in an online survey 3b. Foster child wellbeing using the Strengths and Difficulties Questionnaire total difficulties score (Goodman, 2001) from a local authority administrative data return 4. Carer self-reported family relationships using the SCORE-15 (15 item) (Stratton et al., 2010) in an online survey 5. Number of placements, dates of placement changes, reasons for placement changes (child-level) from a local authority administrative data return
Exploratory outcome(s)	Variables	6. Carer turnover 7. The rate of referrals of children to Child and Adolescent Mental Health Services (CAMHS)
	Measure(s) (instrument, scale)	6. Carer turnover, reason for carer ceasing to be a carer (carer level) 7. Whether a child has been referred to CAMHS between randomisation and end of reporting period

--	--	--

There are a number of outcome measures we could use. We have consulted our advisory committee (four foster carers, two academics and one Fostering Consultant) in finalising our choice of measures for primary data gathering directly from foster families. In line with WRAP’s emphasis on wellbeing, we selected the Warwick Edinburgh Mental Wellbeing Scale as our primary outcome measure .

After consulting with local authorities on our data request, we have selected variables that are accessible for local authorities. Referrals to CAMHS may prove challenging due to data availability but local authorities have until March 2024 to address any challenges with sharing this. It is reasonable to assume that placement changes and foster carer turnover are likely to be correlated with poor wellbeing (Rubin et al., 2007;⁵ Adams et al., 2018⁶).

Randomisation

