4. We will work with Barnardo's to explore mechanisms for reminding participants of the endline survey, including social media, via fostering social workers, and at the Keeping Connected groups.
5. We will check whether contact details for participants are up-to-date with local authority records.

In order to minimise data storage and use the most up-to-date contact details, we will obtain contact details for all randomised carers from the Barnardo's Expression of Interest form.

Table 3. Milestones for outcome measure collection

Task	Date
Referrals of families sent by Barnardo's to Coram	March-April 2023
Eligible referred families randomised by Coram, then randomisation outcomes shared with local authorities and Barnardo's	March – April 2023
Coram emails/posts baseline survey to carers (with prompt text message, if mobile phone number available)	March – April 2023
Coram randomises eligible referred families, then emails/posts baseline surveys to carers (with prompt text message, if possible)	March 2023 – March 2024
Coram sends endline survey by email/post to carers (with prompt text message, if mobile phone number available)	1 st July 2024
Coram requests administrative data from local authorities	1 st July 2024
Coram sends reminder email/text message/post to non-respondent carers	July 2024
Deadline for local authorities to send Coram administrative data request Deadline for carers to complete endline survey	31 st July 2024

The online baseline and endline surveys are hosted on Smart Survey. The prompt text message will read:

'Hi, we're Coram. You may remember agreeing to take part in our study of families in Hull and Lincolnshire. Today we emailed you a survey about your experiences as a carer: [link]. Please complete by 30th April. We will send you a £10 voucher if you complete this survey, and we will also send you another £10 voucher if you complete an additional survey in July 2024.'

The reminder text for the endline survey will read:

'Last chance to have your say! We have emailed you a survey about your experiences as a carer. Your response will help Barnardo's and local authorities to offer the best possible wellbeing support to the fostering community. We will send you a £10 voucher if you complete this survey by 31st July. The link to the survey is [link]'

We will also consider including an additional prize draw in a reminder text, dependent on the response rate.

Type	Outcome	Outcome measure	Collected from	Baseline	Endline

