We will request administrative data from local authorities in March 2024. We will follow DfE SSDA903 requirements to the greatest extent possible, to minimise burden. Some data will have the foster child as the unit of analysis, and some will have the carer as the unit of analysis. We will use an Excel template for the data request that will be partially completed with demographic information about carers and children provided at randomisation. This entails routinely collected data on the care status and living arrangements of children, numbers and dates of placement changes, foster carer turnover management information (unique ID of the foster carer and step-down dates), and Strengths and Difficulties Questionnaire (SDQ) total difficulties scores for foster children (and date of the score and the unique ID of the child). We will gather SDQ scores from local authorities in March 2024, which according to published figures should be available for around 84% of looked-after children. A full breakdown of variables is provided in the spreadsheet template in Appendix 2.

For our secondary outcome of **placement changes**, we will seek data on the following variables for each foster child:

1. Number of placements since randomisation

¹⁷ Collins, J., Gibson, A., Parkin, S., Parkinson, R., Shave, D., & Dyer, C. (2012). Counselling in the workplace: How time-limited counselling can effect change in well-being. *Counselling and Psychotherapy Research*, 12(2), 84-92.

¹⁸ Maheswaran, H., Weich, S., Powell, J., & Stewart-Brown, S. (2012). Evaluating the responsiveness of the Warwick Edinburgh Mental Well-Being Scale (WEMWBS): Group and individual level analysis. *Health and Quality of Life Outcomes*, 10(1), 1-8.

¹⁹ Hamilton, E., Carr, A., Cahill, P., Cassells, C., & Hartnett, D. (2015). Psychometric properties and responsiveness to change of 15- and 28-item versions of the SCORE: A family assessment questionnaire. *Family process*, 54(3), 454-463.

2. Date of first placement change since randomisation (if applicable)
3. Nature of second placement (if applicable)
4. Reason for first placement change (if applicable)
5. Other reason for first placement change (if applicable)
6. Date of second placement change since randomisation (if applicable)
7. Nature of third placement (if applicable)
8. Reason for second placement change (if applicable)
9. Other reason for second placement change (if applicable)
10. Date of third placement change since randomisation (if applicable)

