[name], Research Assistant	Administrative research support, such as carrying out randomisation and sending text messages
[name], Research Associate	Freelance qualitative planning and analysis input as needed, as a senior researcher

Timeline

Table 6. Project timeline

Dates	Activity	Staff responsible/leading
September - February 2023	Research ethics application and approval, protocol drafting and revisions, discussion with experts and advisers, What Works for Children's Social Care review draft protocol, drafting and finalising data sharing agreements and memorandums of understanding	Coram
March 2023	Protocol publication	Coram
March 2023	Request carer contact details from local authorities, hold information sessions	Barnardo's
March - April 2023	First batch of randomisations	Coram
March 2023 -- March 2024	Randomisation: subsequent waves (on demand)	Coram
20 th March 2023	Baseline survey sent to carers	[name]
31 st April 2023	Deadline for baseline survey	[name]
April-June 2023	WRAP phase 1 delivery (see intervention protocol)	Barnardo's
May 2023	Observation of WRAP groups	[name]
Aug-Oct 2023	WRAP phase 2 delivery (see intervention protocol)	Barnardo's
July-Sept 2023	First batch of interviews with participants, social workers, and Barnardo's staff	[name]
September 2023	Observation of WRAP groups	[name]
July – September 2023	Interviews with children, carers and professionals	[name]
October 2023	Midpoint meeting with evaluation advisors	Coram

November 2023	Interim report	Coram
Dec 2023-Feb 2024	WRAP phase 3 delivery (see intervention protocol)	Barnardo's
January 2024	Observation of WRAP groups	[name]
March-May 2024	Second batch of interviews with participants, social workers, and Barnardo's staff	[name]
April-June 2024	WRAP phase 4 delivery (see intervention protocol for details)	Barnardo's
April-June 2024	Survey of professionals	[name]
1 st July 2024	Endline survey sent to carers	[name]
1 st July 2024	Request admin data from local authorities, request costs from local authorities and Barnardo's	[name]
31 st July 2024	Deadline for endline carer survey	[name]
31 st July 2024	Deadline for administrative data return and costs from local authorities and Barnardo's	[name]
June – September 2024	Analysis, drafting, revisions, meeting of evaluation advisors	Coram

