- Date of first WRAP session attended
- Number of WRAP sessions attended
- Whether WRAP was received by other members of the household, which members
- Why WRAP did not take place ('refer for WRAP group') or why WRAP did take place ('do not refer' group)? (if applicable)
- SDQ score at randomisation [provided by Coram]
- Date of SDQ at randomisation [provided by Coram]
- Second SDQ score
- Date of second SDQ score
- Version used for second SDQ score
- Number of placements since randomisation (if applicable)
- Nature of second placement (if applicable)
- Reason for first placement change (if applicable)
- Date of second placement change since randomisation (if applicable)
- Nature of third placement change since randomisation (if applicable)
- Reason for second placement change (if applicable)
- Date of third placement change since randomisation (if applicable)
- Nature of fourth placement change since randomisation (if applicable)
- Reason for third placement change (if applicable)
- Referral(s) made to CAMHS since randomisation
- Date of referral(s) to CAMHS (if applicable)
- Reasons for referrals to CAMHS (presenting issues) (if applicable)
- Comments on data (optional)

Final data return – carer-level data:

- Local authority name [provided by Coram]
- Family ID [provided by Coram]
- Child ID [provided by Coram]
- Randomisation outcome 'refer for WRAP' (intervention) group or 'do not refer for WRAP (control) group [provided by Coram]
- Date of randomisation [provided by Coram]
- Number of foster/kinship children in household at randomisation [provided by Coram]
- Number of other (birth) children in household at randomisation [provided by Coram]
- Number of foster/kinship children currently in household
- Number of other (birth) children currently in household
- Reason for changes in number of children in household (if applicable)
- Did the carer receive WRAP?
- Date of first WRAP session attended
- Number of WRAP sessions attended
- Whether WRAP was received by other members of the household, which members

- Why WRAP did not take place (if in 'refer for WRAP group') or why did WRAP take place (if in 'do not refer')
- Has the foster carer ceased fostering? (yes/no/unknown)
- Plans to cease fostering in the next year? (yes/no/unknown)
- Reasons foster carer has ceased fostering/plans to (if applicable)
- Contributing factors
- Comments on data (optional)

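### The protocol gives two dates, March and July 2024, for the administrative data request that in effect closes the SDQ, placement, carer turnover and CAMHS outcome windows

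*Protocol*

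**What the plan says.** The protocol dates the administrative request in three places.

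- **Outcome measures, text on administrative data:** "We will request administrative data from local authorities in March 2024". Later in the same paragraph: "We will gather SDQ scores from local authorities in March 2024".
- **Table 3 (milestones):** "Coram requests administrative data from local authorities", dated 1 July 2024, and "Deadline for local authorities to send Coram administrative data request", dated 31 July 2024.
- **Table 6 (project timeline):** "Request admin data from local authorities, request costs from local authorities and Barnardo's", dated 1 July 2024, with the return again due on 31 July 2024.

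Three other features bear on the choice of date.

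- Tables 3 and 6 both run randomisation from March 2023 to March 2024.
- Table 6 lists "WRAP phase 4 delivery (see intervention protocol for details" for April to June 2024.
- Outcome measures sends the endline survey in July 2024 so that it follows the end of all Level 1 delivery.

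Placement changes, carer turnover and CAMHS referrals are counted from randomisation. The design table closes the CAMHS window at the end of a reporting period to which it gives no date.

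**The concern.** A data request date is often only logistics. Here it does more. The administrative outcomes start at randomisation and have no stated end, so the day the authorities draw the data is the day the outcome window closes. Two request dates therefore mean two definitions of each outcome.

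The two are not equivalent. A March 2024 cut falls as randomisation closes and before the last delivery phase begins. Some intervention-arm exposure would not yet have happened, and the newest families would have had almost no time in which an event could occur. Under intention to treat, both features pull estimated effects towards zero. The reason the protocol gives for holding the endline survey until July applies equally to the SDQ and to placement changes, and a March extraction would defeat it.

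The field list adds a related difficulty. Outcome measures promises the date of the first placement change, the carer's unique ID and the carer's step-down date. The final return in Annex 3 has none of these. It asks for "Date of second placement change since randomisation (if applicable" and for the date of the third change, but not the first. The carer-level list carries a child ID instead of a carer ID, and asks whether the carer has ceased fostering but not when. Without those dates, first placement changes and turnover cannot be trimmed to a common closing date.

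**Working it through.** The documents give no numerical result to reproduce; the check is calendar arithmetic on their own dates.

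**Inputs**

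- Randomisation, March 2023 to March 2024: Tables 3 and 6. (The Procedures section says the first families are randomised in February 2023, which would add about one month to the upper ends below.)
- Candidate cuts: March 2024 (Outcome measures) and 1 to 31 July 2024 (Tables 3 and 6).
- Delivery: phase 3 is December 2023 to February 2024 and phase 4 is April to June 2024 (Table 6).

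**Step 1. Follow-up.** Follow-up in months = (cut date − randomisation date in days) / 30.4375.

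| Randomised on | Cut 1 Mar 2024 | Cut 31 Mar 2024 | Cut 1 Jul 2024 | Cut 31 Jul 2024 |
|---|---|---|---|---|
| 1 Mar 2023 | 12.0 | 13.0 | 16.0 | 17.0 |
| 30 Apr 2023 | 10.1 | 11.0 | 14.1 | 15.0 |
| 1 Jan 2024 | 2.0 | 3.0 | 6.0 | 7.0 |
| 1 Feb 2024 | 1.0 | 1.9 | 5.0 | 5.9 |
| 1 Mar 2024 | 0.0 | 1.0 | 4.0 | 5.0 |
| 31 Mar 2024 | −1.0 (after the cut) | 0.0 | 3.0 | 4.0 |

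From 1 March to 1 July 2024 is 31 + 30 + 31 + 30 = 122 days, and 122 / 30.4375 = 4.0 months. Every family loses about 4 months under the earlier date. The loss is proportionally small for the first entrants (12.0 of 16.0 months kept, 75%) and large for the last (1.0 of 5.0 months kept, 20%, if randomised on 1 February 2024).

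**Step 2. Position against delivery.** A cut between 1 and 31 March 2024 falls

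- 1 to 31 days after phase 3 ends (29 February 2024);
- 1 to 31 days before phase 4 starts (1 April 2024);
- 91 to 121 days before phase 4 ends (30 June 2024).

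A cut between 1 and 31 July 2024 falls 1 to 31 days after phase 4 ends. The March cut contains no phase 4 delivery; the July cut contains all of it.

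**Step 3. Which analyses depend on the date.** Among the five secondary measures (peer support, BAC, SDQ, SCORE-15, placement changes), two are administrative: SDQ and placement changes. Both exploratory outcomes, turnover and CAMHS referral, are administrative. The Analysis of harms section rests on the change in SDQ and so uses the same return. The primary outcome, WEMWBS, comes from the carer survey, which is July 2024 throughout.

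**Step 4. What the return would allow.** I take Annex 3 as the operative field list.

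| Item | Dated in the Annex 3 final return? |
|---|---|
| Second SDQ | Yes |
| CAMHS referral | Yes |
| Second and third placement change | Yes |
| First placement change | No |
| Carer ceasing to foster | No |

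The size of the first-change gap can be judged from figures the Randomisation section cites for children in care over one year: 32% had at least one move and 10% at least two. The share of movers with exactly one move is (32 − 10) / 32 = 69%. If that pattern held here, about two thirds of children who move would have no change date in the return.

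**The case against.** The strongest reply is that this is a drafting slip. Both timetables agree to the day on request and deadline, the primary outcome is untouched, and this is a pilot. That is fair on how the conflict probably arose. It does not remove it: the March date is stated twice in the paragraph that specifies the request, and nothing describes two separate requests.

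A reader might also infer more than the documents support.

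- **That late-randomised families would have no follow-up.** This is true only for those randomised in March 2024 (0 to 1 month). January and February 2024 entrants would have about 1 to 3 months. Outcome measures expects most families to enter in March 2023.
- **That a quarter of intervention families would be untreated at a March cut.** Phases are not defined as cohorts of families. Phase 1 concentrates on carers and social workers, so members of one family may attend in different phases. The phase detail is in an intervention protocol that is not part of this document.
- **That the arms would be biased against each other.** Both arms would share the same cut. The consequence is shorter exposure and attenuation.
- **That the return could not be re-cut at all.** SDQ scores and CAMHS referrals are dated and can be truncated to an earlier day. The gap is confined to first placement changes and turnover. No date field could extend a March return forward; that would take a second request.
- **That authorities would work to different dates.** One evaluator issues one template to all three, and nothing points to staggered requests.
- **That the design section also conflicts.** It says "local authorities have until March 2024 to address any challenges with sharing this" about CAMHS data. A March deadline for resolving sharing problems is compatible with a July request.

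On the Annex 3 gaps, one may answer that carer IDs are collected at randomisation and that the template is to be part-filled from that information. This softens the missing carer ID but supplies neither missing date.

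How to model unequal time at risk is a matter for the analysis plan and is not part of this point.

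**Conclusion.** The point holds as an unreconciled contradiction in the current text about when the administrative data are drawn. Because no other end of reporting is given, it leaves the outcome window undefined for SDQ, placement changes, carer turnover, CAMHS referrals and the SDQ harms analysis.

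Following the text instead of the tables would shorten follow-up by about 4 months for every family, to about 0 to 12 months instead of 4 to 16. It would exclude all phase 4 delivery and leave the last entrants with little or no follow-up. The direction is attenuation of intention-to-treat effects. Its amount cannot be computed, because the protocol does not say how many families will enter late or receive WRAP in phase 4. With most families expected in March to April 2023, the average loss of follow-up in proportion to the total should be nearer the early-entrant figure than the late one.

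The Annex 3 omissions are real but narrower: three promised items, two of them dates needed to apply a common cut to placement changes and turnover.

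The conclusion assumes a single final return, which is what Annex 3 describes, and randomisation continuing to March 2024, as both tables state; two text passages say only early 2024.

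**What to change.** 1. In Outcome measures, replace both March 2024 statements with the 1 July 2024 request date of Tables 3 and 6, which matches the endline survey.
2. State one end-of-reporting date that applies to all three authorities and to every administrative outcome, and refer to it in the CAMHS definition in the design table. A request on 1 July with return by 31 July otherwise still leaves up to 30 days open.
3. Add to the Annex 3 final return the date of the first placement change (child level), and the date the carer ceased fostering and the carer ID (carer level). Outcome measures already promises all three.

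The cost is a text correction and three template fields, made before the request is issued. No change to the design, sample size or primary analysis is needed.

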11. Nature of fourth placement (if applicable)
12. Reason for third placement change (if applicable)
13. Other reason for third placement change (if applicable)

In the guidance provided with the data return, we will ask local authorities to provide reasons for placement changes experienced by foster children in randomised households, according to the following categories (taken from the [SSDA903 return](#), DfE, 2022²⁰):

1. Change to/Implementation of Care Plan for child e.g. a planned change of placement which is a part of the child's care plan on a temporary or permanent basis
2. Allegation (s47) – child is removed from placement due to an allegation which is being investigated under s47
3. Standards of care concern – child is removed from placement by authority or provider due to concerns about standards of care
4. Carer(s) requests placement end due to child's behaviour – placement has broken down or been disrupted due to the child's behaviour
5. Carer(s) requests placement end other than due to child's behaviour – intended placement was a short or long-term arrangement but has been broken down or disrupted and carer has asked for the child to be moved
6. Child requests placement end – intended placement was a short or long-term arrangement but has been broken down or disrupted and child has requested to be moved
7. Responsible/area authority requests placement end – intended placement was a short or long-term arrangement but responsible authority has decided the placement no longer meets the needs of the child.
8. Custody arrangement – where child has been admitted into custody
9. Resignation/ closure of provision - child had to be moved because foster carer resigns or setting closes
10. Change in the status of placement only – change in status of placement but the child remains with same carer and there is no change to the care plan
11. Approval removed – a setting is no longer approved/registered with the appropriate statutory body (e.g. Ofsted)
12. Other reasons
13. Unknown reasons

²⁰ Department for Education (2022). Children looked-after by local authorities in England Guide to the SSDA903 collection 1 April 2021 to 31 March 2022 – Version 1.3. Crown Copyright: London.

If any 'other' reason is provided for multiple children, we will create a category code for this response.

For the exploratory outcome of **foster carer turnover** we will ask local authorities to provide the following data in their data return:

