We may exclude some foster placement changes and foster carer turnover according to the reasons for these. This will be agreed in due course and informed by consultation with local authority data leads and our advisors. We anticipate using the following categorisations for analysis:

Include in or exclude from analysis	Reason for placement change	Reason for foster carer turnover
Include	Change to/Implementation of Care Plan for child e.g. a planned change of placement which is a part of the child's care plan on a temporary or permanent basis	Resignation
	Allegation (s47) – child is removed from placement due to an allegation which is being investigated under s47	Uncontested termination of approval
	Standards of care concern – child is removed from placement by authority or provider due to concerns about standards of care	Other reasons
	Carer(s) requests placement end due to child's behaviour – placement has broken down or been disrupted due to the child's behaviour	
	Carer(s) requests placement end other than due to child's behaviour – intended placement was a short or long-term arrangement but has been broken down or disrupted and carer has asked for the child to be moved	
	Child requests placement end – intended placement was a short or long-term arrangement but has been broken down or disrupted and child has requested to be moved	
	Responsible/area authority requests placement end – intended placement was a short or long-term arrangement but responsible authority has decided the placement no longer meets the needs of the child.	
	Custody arrangement – where child has been admitted into custody	
	Other reasons	
Exclude	Resignation/ closure of provision - child had to be moved because foster carer resigns or setting closers	Contested termination of approval
	Change in the status of placement only – change in status of placement but the child remains with same carer and there is no change to the care plan	

	Approval removed – a setting is no longer approved/registered with the appropriate statutory body (e.g. Ofsted)	
--	---	--

Treatment of missing data

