- dummy variable for gender of foster carer or kinship carer (female, male, neither, unknown);
- dummy variables for ethnic group of foster carer or kinship carer (Asian, Black, Mixed, Other, White, unknown);
- dummy variable for age of foster carer or kinship carer (21-24, 25-34, 35-44, 45-54, 55-64, 65-74, 75-84, 85 and over, unknown);
- dummy variable for whether a single carer or couple (single, partner, unknown);
- deprivation indicator (derived from postcode district);
- baseline WEMWBS score;
- time from randomisation (in months).

If any of the cells defined as above have fewer than 10% of cases, we will merge them with another cell.

We may also include time from first session of intervention in our analysis to explore whether the time between participation and survey completion is associated with outcomes.

Secondary outcomes analysis

Regression models will be used to analyse secondary outcomes. For the majority of outcomes, these will also be linear regression models. We will also run a Poisson regression, and zero-inflated Poisson regression as sensitivity tests in the event that the data contains a substantial number of zeroes. Our approach to reporting on baseline characteristics and adjusting for missing data will be the same as those outlined above. The models used for each secondary outcome are outlined below:

- Carers' perceived peer support: Linear regression (with zero-inflated Poisson regression)
- Mental health of children in household: Linear regression
- Carers' family relationships: Linear regression

For our placement changes outcome, we will analyse this according to our pre-specified reason categories but for robustness will also explore the impact on point estimates and effect sizes when alternative categories are used. For example, we may run a logistic regression where any placement change is included as a placement change regardless of the reason for the change.

The mental health of children will be analysed separately as measured by the BAC and the SDQ. As the SDQ is only available for foster children, this sample size will be smaller i.e. no kinship or birth children. Following What Works for Children's Social Care statistical analysis guidance, our secondary outcomes will be adjusted for multiple tests using the Hochberg's step-up procedure for all secondary analyses.

Other evaluation questions

Exploratory analysis

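### The anticipated definition of a placement change excludes moves caused by carer resignation, so a stability gain through carer retention would not show in the secondary analysis

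*Protocol*

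**What the plan says.** The secondary question in Specific evaluation questions (Impact evaluation) concerns the rate of placement changes, with no restriction by reason.

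The Data cleaning section of the Analysis plan then sorts reasons into an include row and an exclude row. The exclude row for placement changes holds three entries: resignation or closure of provision, described as "child had to be moved because foster carer resigns" or the setting closes; removal of approval; and changes of status in which the child stays with the same carer. In the turnover column of the same table, resignation is in the include row.

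The table is provisional. It is introduced by "We anticipate using the following categorisations for analysis", and on whether to exclude reasons at all the section says "This will be agreed in due course and informed by consultation with local authority data leads and our advisors". The reason list under Outcome measures ends with a thirteenth code, "Unknown reasons", which appears in neither row.

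Secondary outcomes analysis treats the categories as settled: "we will analyse this according to our pre-specified reason categories but for robustness will also explore the impact on point estimates and effect sizes". An analysis of all moves regardless of reason is given as an example of what may be run. All secondary analyses are adjusted by Hochberg's procedure.

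**The concern.** Resignation occurs after randomisation and lies on a route by which WRAP could work. The primary outcome is carer wellbeing, and the text after the Design table says that "placement changes and foster carer turnover are likely to be correlated with poor wellbeing". Turnover is itself a trial outcome. A main definition that filters on resignation removes part of the effect that the question asks about: a child who lost the placement because the carer gave up fostering has no counted move for that event.

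The boundary is also hard to justify from the list itself. Carer requests to end the placement, because of the child's behaviour (code 4) or for other reasons (code 5), are counted. A carer who resigns, so that the child must move (code 9), is not. The three are similar carer decisions with the same consequence for the child.

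Finally, the list is open while allocation is known. Under Randomisation, outcomes go back to the local authorities, and in Annex 3 the final return carries the randomised arm alongside the reason fields. The same authorities' data leads are to be consulted on which reasons count.

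**Working it through.** **No stated figure to reproduce.** The protocol gives no event rate, power or sample size for placement changes. The check is therefore illustrative: what would the outcome show under each definition if WRAP reduced resignations?

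**Inputs**
- Risk of at least one move in a year: 32% (Randomisation section, citing national data on children in care).
- Follow-up: 16 months for families randomised in March 2023 with a data request in July 2024 (Table 3). The Outcome measures text gives March 2024 for the request, and later families have less time, so 12 months is shown too.
- Share *s* of moves due to carer resignation: not given; assumed 5% to 30%.
- Effect of WRAP on resignation: not given; assumed to halve its hazard.
- Other move hazards: assumed equal between arms, constant over time and unchanged after a resignation move.

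**Formulas.** Total hazard over follow-up *T* (years): H = -ln(1 - 0.32) × T. This is 0.386 for 12 months and 0.386 × 16/12 = 0.514 for 16 months.

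Resignation moves counted:
- Control: 1 - exp(-H)
- WRAP: 1 - exp(-H(1 - s/2))

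Resignation moves excluded, later moves still counted:
- Both arms: 1 - exp(-H(1 - s)), so the difference is 0 whatever *s* is.

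**Example, 16 months, s = 30%.** Counted: control 1 - exp(-0.514) = 40.2%; WRAP 1 - exp(-0.514 × 0.85) = 35.4%; difference -4.8 points. Excluded: 1 - exp(-0.514 × 0.70) = 30.2% in both arms.

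**Results (WRAP minus control, percentage points)**

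| Share *s* | 12 months, counted | 16 months, counted | Excluded, either period |
|---|---|---|---|
| 5% | -0.7 | -0.8 | 0 |
| 10% | -1.3 | -1.6 | 0 |
| 20% | -2.7 | -3.2 | 0 |
| 30% | -4.0 | -4.8 | 0 |

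**Does the sign reverse?** Only with a further assumption. If just the first move could count, or follow-up stopped at the resignation move, the difference would be +0.1 to +0.6 points at 12 months and +0.2 to +1.0 at 16 months. If the hazard of a counted move doubled after a resignation move, it would be -0.1 to -0.5 points at 12 months, in favour of WRAP.

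**The case against.** The strongest reply is that this is a choice of estimand. Carer exit is analysed separately as an exploratory outcome with resignation included, so the split avoids scoring one event in two outcomes. The table is provisional, alternative categories will be explored, and a final list could reasonably sit in a statistical analysis plan that is not shown.

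Part of this stands. Retention is not hidden from the trial as a whole, and the exclusion is anticipated, not final. But turnover is exploratory, measured on carers, and does not record what happened to the child's placement. The alternative categories are unspecified, and the all-reason model is only a possibility. Nor is the include row a narrow definition of breakdown: it also contains planned care-plan moves (code 1) and custody (code 8). Being provisional does not help either, because the analysis section relies on the categories as pre-specified.

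Two stronger readings are tempting and are not supported. A reader might infer that a resignation move takes the child out of the risk of a counted move, so that better retention would count against WRAP. The protocol states no first-move-only rule: the data request covers second and third changes with their reasons. A reader might also take the 25% of families in the Exclusion criteria as showing that resignation moves are common. That figure concerns families the criterion would remove if authorities had perfect information. It does not give the share of moves due to resignation among those randomised.

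**Conclusion.** The concern holds as a mismatch between the question and the anticipated main definition. Under that definition, the multiplicity-adjusted analysis of placement changes would not show a gain in stability that arises through carer retention. With the assumed shares of 5% to 30% and a halving of resignations, the part lost is about 0.8 to 4.8 percentage points over 16 months. Both inputs are assumptions, so the figures show the mechanism and a plausible scale, not an expected bias. A reversed sign is not claimed.

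The unassigned unknown code and the undated agreement of the list add avoidable discretion once allocation is known. This is a secondary outcome in a pilot, so the point is moderate, but it should be put right.

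**What to change.** Edit the Data cleaning table so that the main definition counts every move in which the child leaves the randomised carer. This includes resignation or closure (code 9), approval removed (code 11) and unknown reason (code 13). Exclude only the status-only change in which the child stays with the same carer (code 10). State alongside it whether second and third moves count.

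Keep the narrower list as a sensitivity analysis that will be run. Replace "This will be agreed in due course" with a commitment to lock the list before the administrative data return.

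The cost is one table and a few sentences, with no new data. There are two downsides. Code 9 also contains some setting closures unrelated to the carer, which adds noise. A resignation will also contribute to both the placement and the turnover outcomes, which the report should say.
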